6.	Child unable to participate in neuroimaging due to claustrophobia or medical contraindication to MRI including any implanted medical device, dental braces, surgical clips for aneurysms in the head, heart valve prostheses, electrodes or other metallic objects; pregnancy
7.	Healthy control children who were treated in the Neonatal ICU during the newborn period for breathing difficulties.
8.	Healthy control children who were hospitalized for breathing problems in the first 3 months of infancy.
9.	If the child is suffering from an acute illness, he or she will be temporarily deferred.

Number of Research Participants

- Indicate the target number of research participants to be accrued locally.*
 Our goal is to obtain 30 complete data sets (preferably Study group = 20; Healthy control = 10). Due to movement artifact in the MRI, some scan data may not be usable so we may need to enroll up to 35 participants. We may also conduct repeat studies on a subset of up to 5 children (~15%) to establish reproducibility of collected data. Only subjects who checked "yes I agree to be contacted..." on their first signed parent consent form will be approached by phone to ascertain interest in participating in the study a second time. Participants studied twice will be re-consented for the second data collection session.
- If this is a multi-site study, indicate the total number of research participants to be accrued across all sites.*
 N/A

Vulnerable Populations

- Indicate specifically if you will include each of the following special populations by checking the appropriate box:*

 - Adults unable to consent**
 - Minors (infants, children, teenagers)**
 - Wards of the state
 - Foster Children
 - Pregnant Women**
 - Neonates**
 - Neonates of Uncertain Viability**
 - Employees of CWRU or UHHS**
 - Prisoners**
 - Illiterate Individuals**
 - Non-English Speaking**
 - University Students**

- If the research involves individuals that are included in a vulnerable population, describe the additional safeguards included to protect the rights and welfare of the individuals for each population indicated.*

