The flyer will indicate that we are conducting a study on brain activity in school age children and that we wish to enroll a broad representation of children. Parents would then be asked to contact us if they would be interested in taking part in the study. This strategy would allow us access to a large pool of potential controls who meet eligibility requirements. Using an IRB-approved telephone script, our research staff will then contact the parents of the child. The purpose of the telephone call will be to further explain the study to the parents, confirm their interest in taking part, and determine their child's eligibility. We are prepared to discuss any aspect of a child's participation at greater length, including research participant rights. Telephone numbers of the study PIs are provided to those asking for more or different information.

The term-born healthy control participants are selected based on eligibility criteria (between 9 and 17 years old; without diagnosis of autism, epilepsy, metallic implants, dental braces, or those who've been treated for a concussion) and approximately matched to study children based on age. All healthy control candidate participants will have been of normal birth weight (> 2500 grams) and with gestational age > 37 weeks.

Additionally, we will exclude children from the healthy control group if they were treated in the neonatal ICU during their birth hospitalization for breathing problems or were hospitalized for breathing problems in the first 3 months of infancy. Children in special education programs will not be excluded as controls. Both groups of children are expected to be in generally good physical health, although we anticipate that the group of preterm-born children may have more chronic conditions (e.g. asthma) and more health-related functional limitations than the term group.

Setting

1. *Describe the sites or locations where your research team will conduct the research.*
2. *Identify where your research team will identify and recruit potential research participants.*
3. *Identify the physical location where research procedures will be performed.*

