- Health plan beneficiary number
- Account number
- Certificate/license number
- Any vehicle or other device serial
- Device identifiers or serial numbers
- Web URL
- Internet protocol (IP) address
- Finger or voice prints
- Photographic images
- Other: Any characteristic that would uniquely identify the individual

2. *List all other data to be collected for the research study (e.g. laboratory values, physician notes, length of stay, etc.).*

- Magnetic Resonance Imaging, specifically T1 structural scan, Diffusion Tensor Imaging (DTI), and functional Magnetic Resonance Imaging-Blood Oxygen Level Dependent (fMRI-BOLD)
- High density electroencephalography (HD-EEG)

- Neurobehavioral Assessments of child: Verbal n-back; Grooved Pegboard task
Parent report of child behavior (parent-report): Child Behavior Checklist, Vanderbilt Assessment Test, Child’s Sleep Habits Questionnaire (for children ages 9-12), Pediatric Sleep Questionnaire (for children ages 9-17).
- Urine collection (to determine pregnancy exclusion for female child participants)

Data Analysis Plan

1. Describe the data analysis plan, including any statistical procedures. Provide a power analysis if applicable.
2. If applicable, describe the primary and secondary study endpoints including safety endpoints.

Our intent in this exploratory cross-sectional two-arm pilot study is to develop sufficient Scientific Rigor to support a future study appropriately powered to account for our proposed primary outcome measures and co-variates. Our sample will include 20 prematurely born children who experienced hypoxic insults during postnatal life. To allow comparison to “normative” expectations, we will compare these 20 former preterm children with 10 healthy term-born controls without exposure to hypoxia and of similar age, sex, race distribution as the preterm group. Data from these 30 children will be used to develop appropriate sample sizes, using actual rather than predictive data, for future studies characterizing neural structure and function following postnatal hypoxic insults.

Specific structural and functional characteristics used in our analyses will include

- apparent diffusion coefficients and fractional anisotropy generated from DTI data
- fMRI-BOLD, measured during the pediatric verbal n-back, and HD-EEG sLORETA

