- neurobehavioral assessment results (grooved pegboard test, verbal n-back, Child Behavior Checklist, Vanderbilt Assessment test, Child’s Sleep Habits Questionnaire, Pediatric Sleep Questionnaire)

Covariates include 1) age, 2) sex, 3) race, 4) preterm vs. term birth, and 5) frequency of hypoxic insults (< 5000 versus ≥ 5000) during the first 8 weeks of life within the preterm group. The continuous outcome measure variables will be summarized using descriptive statistics (mean, standard deviation, median, interquartile range). Frequency analyses and stem-n-leaf graphs will characterize data distributions. Skewed continuous variables will be transformed to satisfy normality assumptions of hypothesis testing. Outcome measures for the two groups will be compared graphically using box plots. We will perform hypothesis tests for equality of data distribution for the two groups using t-tests or Wilcoxon sign rank test, as appropriate, with a significance level of 10%.

As we are interested in the differences of above mentioned outcome measures in two groups, we will focus on effect size estimation for the differences of our measures. To detect significant effect size, we will perform regression analysis on the outcomes of interest with the primary covariate of interest being group membership (preterm vs. term birth). In the regression analyses, we will control only for significant confounding effects of age, sex, race, and frequency of hypoxic insults. Using regression analyses, we will determine point

estimates, regression coefficients (beta), as well as 90% confidence interval of betas. The confidence intervals will be main estimated effect size or the differences in outcomes in two groups due to preterm and term birth.

Confidentiality of Specimens and Banking

I am not storing specimens in this research project – *please leave the rest of this section blank*

Describe:

- The source of the specimens*
- Where the specimens will be stored*
- How long the specimens will be stored*
- How the specimens will be labeled*
- How the specimens will be accessed*
- Who will have access to the specimens*
- When and how will the specimens be destroyed*
- How will the specimens be transported (Please note if transporting specimens, a Material Transfer Agreement (MTA) is required).*

Describe:

- The procedures to release specimens including:*
 - i. The process to request a release*
 - ii. Approvals required for a release*
 - iii. Who can obtain specimens*

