As a token of appreciation of the time and effort made by the parent and child to participate in this study, we will compensate each child who completes the protocol with a \$50 Amazon gift card. Each parent whose child completes the protocol and completes the parent questionnaires will also be compensated with a \$50 gift card [note: only one parent per participating child is eligible]. In special circumstances that require a parent proxy to come with the child to the study visit, the study team, parent, and caregiver will make a decision as to who can best respond to the questionnaires about the child’s activities and behaviors. The parent or the caregiver who completes the questionnaire will be compensated \$50. The total compensation for the child/parent unit is \$100 value. If two children participate from the same family (e.g. one healthy child and one former preterm child OR two healthy OR two former preterm children), they will be eligible for \$100 for each participating child/parent

unit. If a child/parent completes the protocol a second time, the child will receive a \$50 Amazon gift card and the parent will receive a \$50 gift card for completing the re-study.

The \$50 parent/caregiver incentive is also meant to cover expenses of parking during the time of data collection. Both the child and the parent/caregiver will receive their incentives on the day of the data collection visit.

Compensation for Research Related Injury

Describe who will pay for the costs of medical treatment and/or compensation in the event of a research related injury:

- Funding agency is providing some/all payment for injury
- Funding agency is providing no payment for injury
- Not applicable

Provisions to Monitor the Data to Ensure the Safety of Research Participants

1. *Describe the Data and Safety Monitoring Plan for the proposed study. Describe how often the data will be monitored for completeness, accuracy and adherence to the protocol.*
2. *Is there a formal Data and Safety Monitoring Board/Committee? If yes, provide information about the DSMB/C including the contact information of the committee member(s) (as applicable); whether it is independent from the study sponsor; how often it meets; the type of data that will be used; written reports, etc.*

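### The rank test named for the preterm-versus-term comparison is the Wilcoxon signed-rank test, which needs pairs; the design has two unpaired groups of 20 and 10.

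*Combined protocol and SAP*

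**What the plan says.** The Data Analysis Plan states: "We will perform hypothesis tests for equality of data distribution for the two groups". The methods follow in the same sentence: "using t-tests or Wilcoxon sign rank test, as appropriate, with a significance level of 10"%. The qualifier about appropriateness chooses between the two named tests and adds no third.

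The same section fixes the groups: "we will compare these 20 former preterm children with 10 healthy term-born controls". Number of Research Participants gives the same split as a preference ("preferably Study group = 20; Healthy control = 10"). The design is described as cross-sectional with two arms, and under Study Design, Procedures and Timeline each child has one data-collection visit.

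On matching, Recruitment Methods says controls are "approximately matched to study children based on age", and the Data Analysis Plan asks only that the groups have similar distributions of age, sex and race.

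The plan's emphasis is on estimation: "we will focus on effect size estimation for the differences of our measures", by regression on group membership with 90% confidence intervals.

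**The concern.** The signed-rank test ranks the absolute values of within-pair differences, or of deviations from a fixed value in one sample. With two separate sets of children there is no difference to form. The rank test for two independent samples is the rank-sum (Mann-Whitney) test, and the plan does not name it anywhere.

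The plan covers many outcomes: diffusion measures, fMRI, EEG source estimates, a timed pegboard, n-back performance and several questionnaires. With 30 children, some of these may stay unsuitable for a t-test even after transformation. For each such outcome, the only prespecified alternative cannot be run. The analyst would have to substitute an unplanned test after the data are in, or invent a pairing that the plan does not describe. The same sentence does not say whether the t-test is paired or two-sample, so it does not settle the question either.

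**Working it through.** The documents give no power or sample-size calculation, so there is no stated figure to reproduce. The check is whether the test fits the design.

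**1. Is there any pairing in the plan?**
- *Age matching* (Recruitment Methods): approximate and at group level. With 20 and 10 children, one-to-one pairs could use at most 10 of the 20 preterm children.
- *Siblings* (Research Participant Compensation): a family may enter "one healthy child and one former preterm child", but this is a payment rule that also allows two children from the same group. It defines no analysis pairs.
- *Re-studied children* (Number of Research Participants): up to 5 children are measured twice to assess reproducibility. The test in question compares the two groups.
- *Other split*: 20 and 10 is only preferred. Equal groups would still be unpaired, and software would then run the signed-rank test without complaint, pairing children by their order in the file.
- *Regression* (Data Analysis Plan): group membership enters as a covariate, which treats the children as independent.

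None of these supplies pairs.

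**2. Can the named test be run?** On simulated vectors of length 20 and 10, the signed-rank routine in scipy stops with an error because the lengths do not match. The rank-sum test and the two-sample t-test both run on the same data.

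**3. What does the rank-sum test give?** The plan does not state sidedness. Two-sided 10% is assumed, which agrees with the 90% intervals (1 − 0.90 = 0.10). For groups of 10 and 20, U runs from 0 to 10 × 20 = 200. From the exact null distribution, the test rejects when min(U, 200 − U) ≤ 62, with actual size 0.0996. The test is therefore available at almost exactly the planned level.

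For scale, the normal-approximation power of a two-sample comparison is Φ(d/SE − 1.645), with SE = √(1/10 + 1/20) = 0.387 in SD units. The differences d are assumptions, since the documents give none:
- d = 0.5: Φ(1.291 − 1.645) = 36%
- d = 0.8: Φ(2.066 − 1.645) = 66%
- d = 1.0: Φ(2.582 − 1.645) = 83%

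Simulated at d = 0.8 with normal data (20,000 runs), the t-test has 64% power and the rank-sum test 62%.

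**4. What if pairs were forced?** This is illustrative only: effect sizes and distributions are assumed, outcomes are scaled to SD 1, and there are 10,000 simulations per scenario at two-sided 10%. The rank-sum test on 20 versus 10 is compared with the signed-rank test on 10 arbitrary pairs.

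| Outcome | Shift (SD) | Rank-sum, 20 vs 10 | Signed-rank, 10 pairs |
|---|---|---|---|
| Normal | 0 | 9.9% | 8.1% |
| Normal | 0.8 | 62% | 45% |
| t, 3 df | 0 | 10.1% | 8.3% |
| t, 3 df | 0.5 | 52% | 33% |
| t, 3 df | 0.8 | 84% | 60% |
| t, 3 df | 1.0 | 94% | 75% |
| 10% outlier mixture | 0 | 10.2% | 8.4% |
| 10% outlier mixture | 0.5 | 52% | 33% |
| 10% outlier mixture | 0.8 | 84% | 59% |
| 10% outlier mixture | 1.0 | 94% | 74% |

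The mixture is 90% N(0,1) and 10% N(0,16), divided by √2.5. The result of a forced pairing would also depend on which pairs were chosen.

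**The case against.** The strongest reply is that this is a slip of one word. The sentence is about two groups, the next paragraph regresses on group membership, and a reader would take the rank-sum test as intended. At 20 and 10 the mistake also announces itself, because the code fails and no wrong p-value is produced. The branch is narrow: skewed variables are transformed first, the t-test remains available, and no decision rests on the Wilcoxon p-value.

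Most of this stands, and it limits the importance of the point. It does not make the rule executable. The protection from a software error also disappears if the groups end up equal in size.

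A second objection is that the power comparison measures something else. It applies only if an analyst invents pairs, and it mixes two effects. That is correct. Adding a rank-sum test on 10 versus 10 at 0.8 SD separates them (a further 10,000-run simulation, so the end figures differ by about a point from the table):
- Normal: 62% → 49% → 45%. Dropping 10 children costs 13 of the 17 points.
- t, 3 df: 83% → 71% → 61%. Dropping them costs 12 of 22.
- Mixture: 83% → 70% → 59%. Dropping them costs 13 of 24.

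More than half of each loss comes from discarding half the preterm group. The figures show what forced pairing would cost. They are not the size of the defect itself.

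Third, t-tests on two groups of different children can sensibly mean only two-sample tests. This is fair: adding the words is a clarification, not the correction of an error.

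**Conclusion.** The concern holds. The plan names a paired or one-sample test for a comparison of two independent groups, and nothing in the documents supplies pairs or an alternative rank test. This conclusion rests on the design alone and does not depend on any assumed effect size or distribution.

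The consequence is moderate. It affects only the non-parametric branch of the unadjusted comparisons in an exploratory pilot whose main estimate comes from regression. The wording is probably a slip, but a prespecified analysis that cannot be run as written should be corrected, particularly as the pilot is meant to support the design of a later study.

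**What to change.** In the hypothesis-testing sentence of the Data Analysis Plan, replace the signed-rank test with the *Wilcoxon rank-sum (Mann-Whitney) test*, and write *two-sample t-tests* for clarity. The 10% level can stay as it is.

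The cost is two phrases in one sentence. Sample size, procedures, data collection and the regression analysis do not change.

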4. Describe when research procedures will take place and the duration of an individual subject's participation in the study. Use of the descriptive table listing the study procedures that indicates the visit/week of the interventions below is encouraged.

	Pre-Screening	Visit 1	Visit 2	Visit 3	Six week Follow up
Estimated time requirement					
Data Collection	X				
Study Procedure 1		X	X	X	
Study Procedure 2		X		X	
Study Procedure 3		X		X	
Phone Call Questionnaire					x

DESIGN & DESCRIPTION: The investigators will conduct an observational study comparing two groups of children to determine whether differences in birth events and oxygen levels during the newborn period lead to structural and functional impairment within the brain's dopaminergic pathways and the cortical regions innervated by those pathways. The dopaminergic system is involved in modulating motor control and cognitive function.

Our goal is to characterize **structure** and **function** of dopaminergic pathways and the cortical regions innervated by those pathways in post-hypoxic former preterm children. We will accomplish this through the use of neuroimaging analysis techniques, such as

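### The preterm-versus-term regression should use a fixed age, sex and race adjustment and leave out the preterm-only hypoxia term

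*Combined protocol and SAP*

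**What the plan says.** The Data Analysis Plan compares 20 preterm children with "10 healthy term-born controls without exposure to hypoxia", described as "of similar age, sex, race distribution as the preterm group". Group membership is the covariate of main interest in the regressions. For the other covariates, "we will control only for significant confounding effects of age, sex, race, and frequency of hypoxic insults". The hypoxia covariate is binary (below 5000 versus 5000 or more events), counted "during the first 8 weeks of life within the preterm group".

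The result reported is the group beta with its 90% interval: "The confidence intervals will be main estimated effect size". These results feed later planning: "Data from these 30 children will be used to develop appropriate sample sizes, using actual rather than predictive data".

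Two other sections bear on this. Study Design, Procedures and Timeline states the question as whether "differences in birth events and oxygen levels during the newborn period lead to structural and functional impairment". Recruitment Methods (item 5) describes controls as "approximately matched to study children based on age"; no matching on sex or race is described.

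The plan does not say what makes a confounding effect significant. Its 10% level is attached to the two-group tests. It gives no coding of hypoxia for controls and no separate within-preterm model.

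**The concern.** One sentence raises two problems.

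**Hypoxia as a confounder.** A confounder of preterm versus term must vary outside the preterm group and must not be part of the exposure itself. This variable fails on both counts. If it enters the model, the group coefficient answers a different question from the one the plan poses. Because entry depends on significance, the question could also change from one outcome to the next across the imaging, EEG and behavioural measures.

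**Selection by significance.** The groups are not randomised, and with 30 children a significance test can easily miss a real confounder. An interval computed as if the chosen model had been fixed in advance ignores the selection step. The interval is this pilot's main product, so its width and centre matter more than any p-value.

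**Working it through.** The plan gives no power, SD or effect size, so there is no figure to reproduce. Everything below is in units of the outcome SD.

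**1. Baseline precision.** With 20 versus 10, SE = √(1/20 + 1/10) = 0.387. The 90% half-width is 0.659 on 28 residual df. With three balanced covariates (25 df) it is 0.662, so the df cost alone is negligible.

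**2. Hypoxia term, controls coded 0.** Let k of the 20 preterm children have 5000 or more events. The fitted group coefficient is the mean of the 20 − k preterm children below 5000 minus the control mean. It differs from the full preterm-versus-term contrast by (k/20) × the high-versus-low hypoxia difference. Its SE is √(1/(20 − k) + 1/10). The splits and the 0.3 SD difference are assumptions.

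| k | SE | Rise over 0.387 | Shift if always kept (0.3 × k/20) |
|---|---|---|---|
| 6 | 0.414 | 7% | 0.09 |
| 10 | 0.447 | 15% | 0.15 |
| 14 | 0.516 | 33% | 0.21 |

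The plan keeps the term only if significant. Simulating an assumed p<0.10 screen with a 0.3 SD effect, it is retained in about 15–17% of samples. Averaged over all samples, the shift is then about 0.04–0.09 SD (0.10 at k = 14 in one run), roughly half the last column. In the samples that retain the term, the shift is larger than the last column.

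**3. Hypoxia term, controls coded missing.** A complete-case fit drops all 10 controls. Group is then constant, the design (intercept, group, hypoxia) has rank 2 of 3, and the group effect cannot be estimated.

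**4. Missing oxygen data.** Recruitment Methods (item 2) allows preterm children without continuous saturation recordings. They have no value on this covariate and would drop out of any model containing it.

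**5. Choosing age, sex and race.** Simulation of 20 versus 10 with true group effect 0 and 20,000 replicates. Assumptions, none from the documents: within-group age correlation 0.3, age SD 2.6 years, sex and race effects 0.5 SD, cut-off p<0.10. In this table all gaps push the estimate in the same direction.

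| Gap (age in years / sex and race in points) | p-value screen: coverage, bias | Change in estimate (0.10 SD): coverage | All three forced: coverage, bias |
|---|---|---|---|
| 0 / 0 | 87.8%, 0 | 90.6% | 90.2%, 0 |
| 0.5 / 10 | 86.7%, 0.05 | 89.9% | 90.1%, 0 |
| 1 / 20 | 84.1%, 0.10 | 88.8% | 89.8%, 0 |

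Selecting on group imbalance instead gives coverage of 91.2, 90.4 and 89.0%, with bias of 0, 0.09 and 0.13 SD.

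If only the race gap is reversed, bias under the p-value screen falls to about 0.01–0.035 SD. Coverage is still 87.1% and 85.2% in the second and third rows.

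**6. Cost in width.** Mean half-width is 0.615 forced against 0.595 screened with no gap (0.615/0.595 = 1.03). If the covariates have no effect it is 0.694 against 0.645 (1.08).

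**The case against.** The strongest reply is that this is an exploratory pilot. It names its candidate covariates in advance, so age, sex and race give at most eight subsets, and learning which covariates matter is arguably part of its purpose. That stands, and it limits the weight of the point.

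Several stronger readings are tempting, and the documents do not support them:

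- **That selection biases the result by about 0.1 SD.** This needs the age, sex and race gaps all to act in the same direction, and nothing in the plan says they do.
- **That every data-driven rule fails.** Under change in estimate, a recognised meaning of confounding, coverage stays near 89–91% for these gaps.
- **That a fixed set is always more accurate.** With weaker effects (age correlation 0.2; sex and race 0.3 SD) and a 0.5-year/10-point gap, root mean squared error is essentially equal (0.403 and 0.402). The gain there is in honest coverage.
- **That hypoxia moves the estimate by 0.09–0.21 SD.** This assumes the term is always kept, whereas the plan's rule would usually drop it.
- **That the model cannot be fitted.** This holds only if controls are coded missing. The plan calls them unexposed, which points to 0.
- **That the stated similarity of age, sex and race is contradicted.** It is an aim, and approximate age matching is a partial means to it.

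None of this answers the hypoxia point. A low chance of retention does not make the term a confounder, and when it is retained the coefficient answers a different question.

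**Conclusion.** The point holds in two parts.

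The hypoxia part rests on the plan's own definitions and on algebra: the term does not belong in the preterm-versus-term model. Only its size depends on assumptions, namely the split at 5000 events, a 0.3 SD difference and a p<0.10 screen.

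The selection part is conditional. If significance means a covariate p-value, the nominal 90% interval covers about 88% of the time with balanced groups and 84–87% with moderate imbalance, under assumed covariate effects. A fixed set restores about 90%.

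The weight is minor to moderate. The interval half-width is already near 0.65 SD and the study is exploratory, but these estimates are meant to size later work and the repair is cheap.

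**What to change.** Replace the adjustment sentence in the Data Analysis Plan with:

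*All preterm-versus-term regressions include age (continuous), sex and race (two categories, fixed before analysis) regardless of significance, with the same set for every outcome. Frequency of hypoxic insults is not included in this model; it is analysed only within the preterm group, among children with oxygen saturation data.*

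The race grouping should be fixed in advance, because collapsing categories only if cells prove sparse would be another data-dependent rule. Leave the plan's aim of similar age, sex and race distributions in place.

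The cost is 3 of 28 residual degrees of freedom and an interval about 3–8% wider than under p-value screening. Recruitment and data collection do not change.

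### The method behind the main 90% confidence interval is not specified for unequal group variances; with 20 versus 10 children the default regression interval may not cover at 90%

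*Combined protocol and SAP*

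**What the plan says.** All of the following is in the Data Analysis Plan unless another section is named.

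- **Sample.** "Our sample will include 20 prematurely born children who experienced hypoxic insults during postnatal life"; they are compared with "10 healthy term-born controls without exposure to hypoxia". The ratio is 2:1.
- **Main result.** A regression of each outcome on group yields "regression coefficients (beta), as well as 90% confidence interval of betas". These intervals carry the conclusion: "The confidence intervals will be main estimated effect size or the differences in outcomes in two groups due to preterm and term birth".
- **Tests.** The two groups are also compared by t-tests or a Wilcoxon test, "as appropriate, with a significance level of 10" per cent.
- **Variance handling.** None is stated. The plan names no least-squares variant, equal-variance assumption, Welch test, weighting or robust standard error. Skewed variables are to be transformed. SDs and box plots are planned, but no change of method follows from what they show.
- **Expected spread.** Hypoxic-insult frequency is split at 5000 within the preterm group. Under Recruitment Methods, item 5, "we anticipate that the group of preterm-born children may have more chronic conditions (e.g. asthma) and more health-related functional limitations than the term group".

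**The concern.** An ordinary least-squares interval for a group difference uses a single residual variance. With equal group sizes, unequal variances do little harm. With 20 versus 10 the pooled variance is weighted towards the larger group, while the true standard error depends more on the variance of the smaller group. The interval is then too wide if the preterm children vary more and too narrow if the controls vary more. A transformation towards normality does not make the variances equal, and a rank test does not alter the regression interval.

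At stake is the stated error level of the study's main output. The outcomes range from diffusion and BOLD measures to timed tasks and questionnaires. The direction of any imbalance in spread could differ among them, so a method that works in both directions is preferable.

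**Working it through.** **Inputs.** From the Data Analysis Plan: n1 = 20 preterm, n2 = 10 controls, 90% interval (two-sided 10%; the plan does not state sidedness). Assumed: normal outcomes and r = preterm SD / control SD, with the control SD set to 1, because no SD appears anywhere in the documents.

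**Step 1: formulas, group term only.**

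- Pooled variance: (19r² + 9)/28
- Squared standard error used by the interval: pooled variance × (1/20 + 1/10) = pooled variance × 0.15
- True squared standard error: r²/20 + 1/10
- Large-sample coverage: 2Φ(1.645 × √(used/true)) − 1

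**Step 2: numbers.**

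- r = 1: used 0.15, true 0.15, coverage 90.0%. The plan's nominal level is reproduced.
- r = 2: pooled 85/28 = 3.036; used 0.455; true 0.300; √ratio 1.232; coverage 95.7%.
- r = 1.25: pooled 1.382; used 0.207; true 0.178; √ratio 1.079; coverage 92.4%.
- r = 0.8: pooled 0.756; used 0.113; true 0.132; √ratio 0.927; coverage 87.3%.
- r = 0.5: pooled 0.491; used 0.0737; true 0.1125; √ratio 0.809; coverage 81.7%.

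**Step 3: finite-sample coverage, group term only.** The half-width uses t(28) = 1.701 and is averaged over 400,000 chi-square draws of the two sample variances.

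| r | Pooled | Welch |
|---|---|---|
| 0.5 | 81.5% | 89.9% |
| 0.67 | 85.0% | 89.9% |
| 0.8 | 87.4% | 90.0% |
| 1 | 90.0% | 90.0% |
| 1.25 | 92.2% | 90.0% |
| 1.5 | 93.7% | 90.1% |
| 2 | 95.3% | 90.1% |

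**Step 4: with covariates.** Simulation of group + age + sex, 12,000 runs per case:

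| r | Ordinary least squares | HC2, Bell-McCaffrey df |
|---|---|---|
| 0.5 | 82.6% | 88.9% |
| 0.67 | 85.6% | 89.4% |
| 1 | 89.7% | 89.9% |
| 1.5 | 93.2% | 90.4% |
| 2 | 95.0% | 90.9% |

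Mean half-widths, in control SDs:

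- r = 2: 1.18 ordinary versus 1.02 HC2, so 1.18/1.02 = 1.16, or 16% wider than needed.
- r = 1.25: 0.797 versus 0.764, or 4% wider.
- r = 1: 0.677 versus 0.691. Here HC2 costs 0.691/0.677 = 1.02, or 2%.

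The degrees of freedom matter. With three covariates and the ordinary residual t(25), HC2 covers only about 87% to 90%, and HC3 about 91% to 93%.

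**Step 5: how far the expected heterogeneity could push r.** Suppose the preterm group splits evenly into two hypoxia classes whose means differ by d within-class SDs, and the within-class SD equals the control SD (both assumed). Then r = √(1 + d²/4). d = 1 gives 1.12. Reaching r = 1.5 needs d = 2.2, and r = 2 needs d = 3.5.

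**Step 6: carry-over to the next study's size.** If a single pooled variance were carried forward to a 1:1 design, r = 2 would give 3.036 where the average variance is (4 + 1)/2 = 2.5, which is 21% too high. r = 0.5 would give 0.491 where it is 0.625, which is 21% too low. The plan does not say that it will pool; reporting SDs by group removes the question.

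**The case against.** Most of the case on the other side stands as a limit on size.

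- **The plan does not prescribe an equal-variance analysis.** A reader might infer that it does. The text says only regression and t-tests, and Welch's test is a t-test. Pooling is the usual default for an unqualified regression interval; it is not plan text.
- **The preterm mix does not cause under-coverage.** A reader might infer that a heterogeneous preterm group drives coverage to 82% and nearly doubles the 10% error rate. It works the other way: more spread in the larger group makes the interval conservative. The 82% end needs controls with twice the preterm SD. The eligibility rules leave greater control spread open, because a 2-year Mental Development Index below 80 excludes preterm children only (Inclusion and Exclusion Criteria) and special-education pupils may be controls (Recruitment Methods, item 5). Neither rule shows it.
- **The likely effect may be small.** Two hypoxia classes one SD apart imply r of only 1.12. If hypoxia frequency is kept as a covariate, the difference between class means leaves the residual. Asthma and functional limitations say little about the variance of imaging measures.
- **Sizing is affected little by coverage.** The group coefficient stays unbiased, and coverage enters a sample-size calculation only if interval limits are used, which the plan does not state.
- **The study is an exploratory pilot with SDs and box plots planned.** These could reveal unequal spread. However, the plan does not say that the SDs are by group, and attaches no action to either.

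What remains is that the interval named as the main result has no stated variance method, and a better one than the default is available at little cost.

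**Conclusion.** The point holds as an inexpensive improvement to an underspecified analysis. It does not show that the planned analysis is wrong. Under the default least-squares reading, the nominal 90% interval covers about 87% to 92% for an assumed SD ratio of 0.8 to 1.25, and about 82% to 95% for 0.5 to 2. The direction that the plan's own expectations support is over-coverage. A 10% test running at about 18% (100 − 82) is the far end of an assumed range in the opposite direction, and the documents give no evidence for it.

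The figures assume normal outcomes, exactly 20 and 10 complete data sets, and fixed covariates. The plan adjusts only for confounders found significant; that selection was not simulated and could itself change coverage.

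**What to change.** In the Data Analysis Plan:

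1. State that unadjusted t-tests are Welch tests.
2. State that the 90% interval for the group coefficient allows a different residual variance in each group, for example HC2 standard errors with Satterthwaite (Bell-McCaffrey) degrees of freedom. Do not pair HC2 with the ordinary residual degrees of freedom. A model with group-specific residual variances is an alternative.
3. Report SDs separately by group and use them to size the next study.

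The cost is a sentence or two of text, and intervals about 2% wider if the variances are in fact equal. No further participants, data or procedures are needed.
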